
Appendix B2 – Epworth Sleepiness Scale

Epworth Sleepiness Scale

Name: _____ Today's date: _____

Your age (yrs): _____ Your gender (Male = M, Female = F): _____

How likely are you to doze off or fall asleep in the following situations, in contrast to just feeling tired?

This refers to your usual way of life recently.

Even if you haven't done some of these things recently, try to figure out how they would have affected you.

Use the following scale to choose the **most appropriate number** for each situation:

- 0 = no chance of dozing
- 1 = slight chance of dozing
- 2 = moderate chance of dozing
- 3 = high chance of dozing

It is important that you answer each item as best as you can.

Situation	Chance of Dozing (0-3)
Sitting and reading _____	_____
Watching TV _____	_____
Sitting inactive in a public place (e.g., a theater or a meeting) _____	_____
As a passenger in a car for an hour without a break _____	_____
Lying down to rest in the afternoon when circumstances permit _____	_____
Sitting and talking to someone _____	_____
Sitting quietly after a lunch without alcohol _____	_____
In a car or bus, while stopped for a few minutes in traffic _____	_____

THANK YOU FOR YOUR COOPERATION

© M.W. Johns 1990-97. Used under License

Appendix B3 – University of Miami Parkinson's Disease Hallucinations Questionnaire (UM-PDHQ)

The University of Miami Parkinson's disease Hallucinations Questionnaire (UM-PDHQ)

Patient identifier: DATE:			
Severity of hallucinations	Question	A:Features/Comments	B:Score (circle appropriate)
	1. Do you experience hallucinations? (Have you noticed anything unusual about your vision? Have you had any unusual visual experiences? Or ever see/hear/feel/smell/taste things that are not really there or that other people do not see?)	Type: (mark appropriate) 1. Visual 2. Auditory 3. Somatic/Cutaneous 4. Gustatory 5. Olfactory (assess each separately)	0. No hallucinations (skip to Annex) 1. One type only 2. Combination C: Not within the past month, but it has happened in the past
	2. How often do you experience hallucinations?		0 = Only a few times 1 = Occasionally (less than once a week, but continuously) 2 = Often (about once per week) 3 = Frequently (several times per week but < than once per day) 4 = Very frequently (≥ once per day)
	3. On average, how long do the experiences last?		0 = Short Duration (< 1sec) 1 = Medium Duration (< 10secs) 2 = Prolonged Duration (> 10secs)
	4. Do you think what you are seeing/experiencing is real?		0 = Not real 1 = Sometimes real 2 = Always real
	5. How many types of images/sensations do you experience?		1 = One 2 = Few (2 or 3) 3 = Several (more than 3)
	6. How severe/emotionally distressing do you find these images/sensations or visions?		0 = No effect/Friendly 1 = Mildly – produce little distress 2 = Moderately – produce distress and are disturbing and disruptive 3 = Severely – very disturbing (medications may be required)
Total Score (min = 0; max = 14)			

Comments:

Please circle the appropriate answer and provide information		
Quality of hallucinations	7. Have you been diagnosed with any eye disease? (i.e. near or far sight problems, double vision, cataract, glaucoma, retinitis, retinal detachment, diabetic or hypertensive eye disease)	Yes (please describe) No
	8. Was there a recent change in your treatment? Please describe.	Yes (please describe) No
	9. Was this change related to the appearance or change in the characteristics of hallucinations?	Yes No I cannot tell N/A
	10. Do you experience hallucinations while "on" or "off"?	On Off Anytime-not related to on-offs
	11. What do you normally see/feel/hear/smell/taste? If not visual describe here: Voices, Music, tastes, smells, skin related:	Not formed/cannot describe Whole Faces Fragmented faces Whole people Animals Insects/reptiles Objects
	12. Is there anything you can do to make the images/sensations disappear?	Yes No
	13. At what time of the day or under which lighting conditions do you experience hallucinations	A. Specific time During the day/Bright During the night/Dark Dim B. Anytime
	14. When are the images most present?	When eyes are open When eyes are closed No difference N/A (for non-visual hallucinations)
	15. Do the images ever make any sound or noise (for visual hallucinations)?	Yes No N/A (for non-visual hallucinations)
	16. Do images move (for visual hallucinations)?	Yes No N/A (for non-visual hallucinations)
	17. Are the images normal size?	Yes No, smaller than normal No, larger than normal N/A (for non-visual hallucinations)
	18. Are the images transparent or solid?	Transparent Solid N/A (for non-visual hallucinations)
	19. Are the images colored?	Yes No, (black and white) N/A (for non-visual hallucinations)
	20. Is the onset of hallucinations gradual or sudden?	Gradual (appear-disappear slowly) Sudden (appear-disappear suddenly) I cannot tell

Appendix C – Cytochrome P450 Drug Interaction Table

PROHIBITED CYP3A4 INHIBITORS*

HIV antivirals (delavirdine, indinavir, nelfinavir, ritonavir)
amiodarone
cimetidine
clarithromycin
diltiazem
erythromycin
fluvoxamine
grapefruit juice
itraconazole
ketoconazole
nefazodone
suboxone
troleandomycin
verapamil

PROHIBITED CYP2C9 INHIBITORS*

amiodarone
fluconazole
izoniazid

PROHIBITED CYP3A4 INDUCERS*

carbamazepine
efavirenz
nevirapine
phenobarbital
phenytoin
pioglitazone
primidone
rifabutin
rifampin
St. John's Wort
troglitazone

PROHIBITED CYP2C9 INDUCERS*

rifampin
secobarbital

Prohibited moderate and strong inducers of CYP3A4 and CYP2C9 include the lists above but are not limited to the medications and agents listed

From: Flockhart DA. Drug Interactions: Cytochrome P450 Drug Interaction Table. Indiana University School of Medicine (2007). "/clinpharm/ddis/clinical-table/" Accessed [6 Dec 2016].

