- 13) Sporadic use of a benzodiazepine, sleep medication or anxiolytic to improve sleep performance. Stable use at a consistent dose is allowed as long as tremor persists against the background of regular medication use. Use on the evening prior to a study visit is prohibited.
- 14) Use of prescription or non-prescription drugs or other products (i.e. grapefruit juice) known to be strong inhibitors or inducers of CYP3A4 which cannot be discontinued 2 weeks prior to Day 1 of dosing and withheld throughout the study, including primidone
- 15) Concurrent illnesses that would be a contraindication to trial participation, including, but not limited to:
 - a) Severe arterial thromboembolic events (myocardial infarction, unstable angina pectoris, stroke) less than 6 months before screening
 - b) NYHA Class III or IV congestive heart failure, ventricular arrhythmias or uncontrolled blood pressure
 - c) Clinically significant ECG abnormality per the investigator assessment or any of the following:
 - i) QTcF >450 msec (males) or >470 msec (females)
 - ii) PR interval >250 msec
 - iii) Atrioventricular block of second degree or higher, including Mobitz I
 - iv) Persistent sinus bradycardia < 50 beats per minute; persistent means the bradycardia is present on the first ECG and on one repeat ECG performed on another day
 - v) For other ECG findings (e.g., including, but not necessarily limited to, tachycardia, bundle branch block, frequent ectopic beats, etc.) the investigator should send a scanned, identity-blinded copy of the ECG tracing to the study safety representative for review
 - vi) The presence of a cardiac pacemaker does not automatically exclude eligibility. The specifics must be discussed with the study safety representative to make a determination of eligibility.
 - d) Known infection with HIV, hepatitis B, or hepatitis C, unless curative therapy completed for hepatitis C with negative PCR
 - e) Significant hepatic (AST/ALT > 2X upper limit of normal) or renal disease (creatinine clearance <39 mL/min)
 - f) Significant psychiatric history including mood disorders and alcohol or substance abuse within the last year
 - g) A current C-SSRS score of 4 or 5 at screening, or history of suicide attempt at any time during the past year
 - h) Clinically significant impaired balance or is considered at increased risk for falls
 - i) Symptomatic orthostatic hypotension

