6.4 Withdrawal of Subjects and/or Discontinuation of Treatment

A subject should be withdrawn from the study for any of the following:

- 1) Withdrawal of subject consent
- 2) Subject is lost to follow-up
- 3) Investigator determines that withdrawal from the study is in the best interest of the subject.
- 4) Subject is non-compliant with protocol-mandated activities.
- 5) Occurrence of any intercurrent condition, injury, or disease that becomes apparent during the study and necessitates the termination of the subject from the study.
- 6) Administrative reason (e.g., termination of the clinical study by a regulatory agency or the sponsor)

A subject should be discontinued from treatment for any of the following:

- 1) Subject is not at least 75% compliant with study drug administration at any study visit ([Section 4.4.](#))
- 2) Occurrence of defined unacceptable toxicity ([Section 4.5](#))
- 3) Investigator determines that discontinuation of treatment is in the best interest of the subject.
- 4) Occurrence of any intercurrent condition, injury, or disease that becomes apparent during the study and necessitates the discontinuation of treatment.
- 5) Pregnancy
- 6) Subject requires use of prohibited concurrent medication
- 7) Subjects answering "yes" to Suicidal Ideation item 4 or 5 on the C-SSRS during the study must be withdrawn from the study treatment. Investigators should also withdraw subjects from treatment if, in the judgment of the investigator, the subject develops other indicators of significant risk of suicide. In the event that suicidal ideation is observed in any study subject, the investigator will manage the situation as he/she deems medically and psychiatrically appropriate.

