14. TETRAS ADL: A 12 item scale where each item is rated on a 0 to 4 scale, with 0 representing normal activity and 4 representing severe abnormality. The sum of the individual scores provides the overall score, ranging from 0 to 48. At Visit 1, the TETRAS ADL subscale should be performed after the TETRAS Performance subscale (performed during a window of 1 to 3 hours after administration of study drug in the clinic) and Kinesia ONE accelerometry and prior to administration of study drug in the clinic. At Visits 3 and 4, the TETRAS ADL should be performed after the TETRAS Performance subscale and Kinesia ONE accelerometry. (Section 8.1.2)
15. QUEST: a 30-item quality of life questionnaire (Section 8.3.1)
16. The Clinical Global Impression Severity (CGI-S) will be administered at Visit 1. The Global Clinical Impression Improvement (CGI-I) will be administered at Visits 3 and 4. (Section 8.3.2)
17. The Patient Global Impression of Change (PGIC) will be administered at Visits 3 and 4. (Section 8.3.3)
18. Subjects will identify 3 specific, personal goals at Visit 1. Progress towards the goals will be assessed via Goal Attainment Scaling (GAS) at Visit 4. (Section 8.3.4)
19. The Epworth Sleepiness Scale is intended to measure daytime sleepiness. (Section 10.1.10)
20. C-SSRS identifies behaviors that may be indicative of an individual's intent to commit suicide. Subjects answering "yes" to Suicidal Ideation item 4 or 5 on the C-SSRS during the study must be withdrawn from the study treatment. (Section 10.1.9)
21. The UM-PDHQ is a 20-item clinician-administered questionnaire that quantitatively and qualitatively assesses hallucinations. The UM-PDHQ will be completed for any subject who reports hallucinations. (Section 10.1.11)

22. Collection of samples will occur pre-dose on Visits 2, 3, and 4. Additionally, at Visit 4, a post-dose sample will be collected as close to 4 hours post-dose as possible, but within the window of 4-6 hours post-dose (i.e., a total of two PK samples are collected at Visit 4. [\(Section 9.1\)](#))
23. A sample for pharmacogenomic testing will be collected in all subjects except where prohibited by local regulation. [\(Section 9.3\)](#)
24. Concomitant medications will be recorded from the time of informed consent through the End of Study. See [Section 7.3](#) for a list of prohibited and restricted medications. At each visit, the study site staff will re-confirm the dose and schedule of other anti-ET drugs the subject is taking.

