7.3 Concomitant Medications and Other Restrictions

7.3.1 Concomitant Medications

Subjects may not be using more than one anti-tremor medication at the time of entry into the study. Subjects must have been on a stable dose for one month prior to screening and must have no change in dose in concurrent anti-tremor medication for the duration of the study. It should be noted that primidone is not a permitted anti-tremor medication.

Subjects may not use medications that might produce tremor or interfere with the evaluation of tremor, such as but not limited to: CNS-stimulants, lithium, amiodarone, metoclopramide, theophylline, and valproate.

On study visit days, subjects must refrain from use of medication/substance(s) that might produce tremor or interfere with the evaluation of tremor, such as but not limited to stimulant decongestants, beta-agonist bronchodilators, caffeine, alcohol and tobacco.

The stable use of a benzodiazepine, sleep medication or anxiolytic to improve sleep performance is allowed as long as tremor persists against the background of regular medication use. Subjects should not use sleep aids on the evening prior to a study visit.

The use of prescription or non-prescription drugs or other products (i.e. grapefruit juice) known to be strong inhibitors or inducers of CYP3A4 must be discontinued 2 weeks prior to Day 1 of dosing and withheld throughout the study. Subjects taking primidone for treatment of their ET may continue to do so at a stable dose. Subject randomization will be stratified by concomitant anti-tremor medication use and site type.

See [Appendix C](#) for a complete list of restricted inhibitors and inducers.

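### Exclusion 14 and the Section 7.3.1 washout cover only CYP3A4 agents, while Appendix C also prohibits CYP2C9 agents, so two or three prohibited drugs are neither excluded nor washed out

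*Protocol*

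**What the plan says.** All references are to the current version of the protocol, which plans about 106 subjects.

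- **Section 6.3, exclusion 14** (same scope in the Synopsis) bars products "known to be strong inhibitors or inducers of CYP3A4 which cannot be discontinued 2 weeks prior to Day 1 of dosing" and adds primidone by name. It does not mention CYP2C9 or Appendix C.
- **Section 7.3.1** states the washout for products "known to be strong inhibitors or inducers of CYP3A4 must be discontinued 2 weeks prior to Day 1 of dosing". It ends by sending the reader to Appendix C "for a complete list of restricted inhibitors and inducers". It also contains a sentence allowing subjects on primidone to stay on a stable dose.
- **Appendix C** has four lists. Two are headed "PROHIBITED CYP2C9 INHIBITORS" and "PROHIBITED CYP2C9 INDUCERS". Its closing note is "Prohibited moderate and strong inducers of CYP3A4 and CYP2C9 include the lists above but are not limited to the medications and agents listed".
- **Table 3, footnote 3** sets the entry test as the criteria in Sections 6.2 and 6.3, confirmed by a central reviewer.
- **Table 3, footnote 24**: "Concomitant medications will be recorded from the time of informed consent through the End of Study", with a pointer to Section 7.3 for prohibited and restricted drugs.
- **Section 6.4, treatment discontinuation item 6**: "Subject requires use of prohibited concurrent medication".

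**The concern.** The list of drugs a subject may not take is wider than the rule that decides who may enter. A subject on fluconazole, for example, passes exclusion 14 as worded and has no stated two-week washout, yet is taking a drug that Appendix C prohibits.

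If that subject is dosed, still needs the drug, and Appendix C is taken as the list of prohibited drugs, Section 6.4 item 6 calls for stopping study treatment. The reason would have been known at screening, and Section 6.4.2 says such subjects are not replaced. Sites could also apply different rules, depending on whether they work from Section 6.3 or from the appendix.

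**Working it through.** No sample-size, power or alpha figure is involved. The check is a count of list entries and a comparison of the rules.

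**Count, from Appendix C**

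- CYP3A4 inhibitors: 14 lines (the HIV antivirals are one line)
- CYP2C9 inhibitors: 3 lines (amiodarone, fluconazole, izoniazid)
- CYP3A4 inducers: 11 lines
- CYP2C9 inducers: 2 lines (rifampin, secobarbital)
- Total: 14 + 3 + 11 + 2 = 30 lines
- Listed twice: amiodarone and rifampin, so 30 − 2 = 28 distinct entries
- CYP2C9 lines: 3 + 2 = 5. Amiodarone and rifampin are also on the CYP3A4 lists, so 5 − 2 = 3 appear only under CYP2C9: fluconazole, izoniazid and secobarbital (3 of 28).
- If the barbiturate screen removes secobarbital: 3 − 1 = 2.

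**The rules for those three drugs**

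| Place | Covers CYP2C9-only drugs? |
|---|---|
| Exclusion 14 (Synopsis, 6.3) | No |
| Section 7.3.1 washout sentence | No |
| Section 7.3.1 pointer to Appendix C | Restricts them, but states no washout for them |
| Appendix C | Yes, prohibited |
| Section 6.4 item 6 | Only if Appendix C defines what is prohibited; it cites no list |

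**Does the pointer in Section 7.3.1 settle it?** There are two readings. If the pointer widens the washout to everything in Appendix C, Section 7.3.1 is stricter than exclusion 14. If it does not, the washout is narrower than the list it points to. Exclusion 14 has no pointer on either reading, and Table 3 footnote 3 ties entry to Sections 6.2 and 6.3. Section 7.3.1 also calls the list complete, while the appendix says its inducers are not limited to those shown.

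**Does the result depend on how a drug is graded?** No. The three drugs fall outside the wording because of the enzyme they are listed under, whatever their strength.

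**The case against.** The strongest reply is that the prohibition can be reached before anyone is dosed. Footnote 24 has medications recorded from consent and sends the site to Section 7.3, and Section 7.3.1 sends it on to Appendix C. Section 5.2 then has a central reviewer check an eligibility checklist for every subject, with no randomization or dosing before clearance. Inclusion 10 adds sponsor medical approval. For the mismatch to matter, all of these would have to pass a drug printed under a prohibited heading. This stands as mitigation, and it means that randomization on such a drug is possible but not expected. It does not remove the conflict: the contents of the checklist are not shown, Section 7.2.1 leaves details of the eligibility review to an Operations Manual that is also not shown, and no eligibility criterion names CYP2C9 agents or Appendix C.

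Secobarbital is probably caught by the barbiturate screen in exclusion 11, since a drug prohibited in Appendix C is hardly an allowed prescription. That is largely right, though Section 10.1.6 words the exception as an approved prescription, which is looser. Fluconazole and izoniazid are not among the substances screened.

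A reader might also infer from the appendix note that moderate CYP3A4 inducers escape exclusion 14. The documents do not support this. In the phrase used there, strong may qualify only the inhibitors, in which case inducers of any strength are covered. No drug on the list can be shown to escape without a potency grading that the protocol does not give.

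**Conclusion.** The conflict holds for the CYP2C9 agents. Fluconazole and izoniazid, and secobarbital unless the urine screen stops it, are prohibited by Appendix C but are neither excluded nor given a two-week washout by the eligibility wording. That is two or three of 28 distinct entries. The count rests only on which list each drug appears under.

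Stronger conclusions do not follow. A reader might infer that subjects on these drugs will be enrolled and then withdrawn. The review steps may stop them first, and a subject who can give up the drug does not clearly meet Section 6.4 item 6. A reader might also infer harm to the primary comparison. The number of subjects affected cannot be derived, the effect of CYP2C9 agents on CX-8998 exposure cannot be judged from the visible text, and no change in power or alpha is shown. Section 11.3 already allows for dropouts. This is an inconsistent eligibility rule, worth correcting because the correction is cheap.

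**What to change.** - **Exclusion 14 (Synopsis and Section 6.3) and the Section 7.3.1 washout sentence:** refer to any CYP3A4 or CYP2C9 inhibitor or inducer prohibited in Appendix C, primidone included, and to any other strong CYP3A4 inhibitor or inducer. Keep the present condition that the drug be stopped two weeks before Day 1 and not taken during the study.
- **Section 7.3.1:** describe Appendix C as a non-exhaustive list. Delete the sentence letting subjects on primidone continue at a stable dose. Otherwise the amended paragraph would contradict itself, because Appendix C lists primidone and the same section says it is not permitted.
- **Section 6.4 item 6:** cite Section 7.3.1 and Appendix C, so that prohibited has one meaning.

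The cost is wording in four places (Synopsis, 6.3, 7.3.1, 6.4), an update of the eligibility checklist and slightly narrower eligibility. No visits, data or subjects are added.
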